8.1.4. Progression Disease

When the progression disease will be confirmed by mRECIST criteria and/or by principal investigator judgement these samples are strongly recommended to be collected:

- Tumor tissue from a rebiopsy, if clinically feasible and patient accepts this procedure
- Blood samples
- Pleural effusion liquid (when feasible)

8.1.5. End of treatment and first follow up visit

End of treatment is defined as the day of discontinuation of the treatment. The reason for end of treatment should be registered in the medical chart.

A safety follow-up visit must be done within 30 days (± 3 days) after the last dose of treatment or immediately before the initiation of any other anticancer therapy. If the **reason for the end of treatment is progression** the following procedures can be performed during the end of treatment visit and should be always conducted between the end of treatment and the initiation of the next treatment. The following procedures must be performed in the safety follow-up visit (or at the end of treatment when the cause is tumor progression):

1. Physical examination, including skin inspection and collection of weight, ECOG, temperature, blood pressure and oxygen saturation.
2. Laboratory testing:
 - **Hematology and coagulation:** WBC count, neutrophils, hemoglobin, platelet count, PT, INR and APTT.
 - **Biochemistry:** Ca, Mg, Na, K, Glucose, ALT, AST, LDH, total bilirubin, alkaline phosphatase, creatinine and clearance of creatinine calculated by Cockcroft-Gault formula, total protein, albumin, amylase, lipase.
 - **Thyroid function:** thyroid-stimulating hormone (TSH). Total or free T3 and total or free T4 must be analyzed if TSH result is out of ULN or LLN.
 - **Pregnancy Tests:** A serum or urine pregnancy testing is required.
 - **Urine test:** A urine testing (dipstick is allowed) is required for proteinuria.

3. Electrocardiograms: A 12-lead ECG is required at screening and as clinically indicated. ECGs should be obtained on the same machine whenever possible. Lead placement should be as consistent as possible. ECG recordings should be performed after the patient has been resting in a supine position for at least 10 minutes. For safety monitoring purposes, the investigator must review, sign, and date all ECG tracings. Paper copies of ECG tracings will be kept as part of the patient's permanent study file at the site. Any morphologic waveform changes or other ECG abnormalities must be documented on the eCRF.
4. Adverse events: Changes from baseline abnormalities (new or worsened clinically significant ones) should be recorded as adverse events on the Adverse Event eCRF until this visit. For laboratory parameters, only grade 2 events will be reported as an AE. All the other events not related to laboratory values will be reported from grade 1. SAEs and AESIs must be recorded and followed from the subject written informed consent signature to 30 days from last dose of treatment.
5. Concomitant medications: Changes from baseline should be recorded on the eCRF until this visit (30 days from last dose of treatment).
6. Tumor assessment: if the end of treatment reason is other than disease progression the CT SCAN schedule will be performed every 8 weeks:

- a. **Chest and abdomen CT SCAN** with oral/IV contrast (unless contraindicated) to determine measurable disease according to mRECIST v1.1.

It is not mandatory to perform the tumor assessment in first follow up visit if the end of treatment reason is other than progression disease and a tumor assessment has been performed in the previous 8 weeks.

After the safety follow up visit, all the patients will be followed by a telephone call every 3 months until the end of study participation or last patient last visit.

End of study participation of the patients included in the study will be the date of the last study assessment.

9. Investigational Medicinal Product

Bintrafusp alfa (M7824) is the Investigational Medicinal Products (IMP) used in this trial. Merck will provide the IMPs at no cost for this trial.

Complete details of the trial drug logistics, distribution, packaging, labelling, storage and handling as well as accountability are described in the **BIMES drug supply manual** that will be provided in the Pharmacy site file to all the participant sites.

Description of the Investigational Medicinal Products

Bintralusp alfa (M7824) is a bifunctional fusion protein composed of the extracellular domain of the transforming growth factor β (TGF- β) receptor II (a TGF- β "trap") fused to a human immunoglobulin G1 antibody blocking programmed death-ligand 1 (PD-L1).

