13.1. Definition of an Adverse Event (AE) and AE's reporting

The main criterion for tolerability is the occurrence of toxicities and Adverse Events (AEs). [REDACTED]

[REDACTED]

[REDACTED]

[REDACTED]

[REDACTED]

[REDACTED]

An adverse event can therefore be any of the following:

Any unfavorable and unintended sign (including an abnormal laboratory finding) (see **NOTE 1** below), symptom, or disease temporally associated with the use of a medicinal product, whether or not considered related to the medicinal product.

Any new disease or exacerbation of an existing disease (a worsening in the character, frequency, or severity of a known condition), except events that are clearly consistent with the expected pattern of the disease progression. These data will be captured as efficacy assessment data only. If there is any uncertainty as to whether an event is due to disease progression, it should be reported as an adverse event.

Recurrence of an intermittent medical condition (e.g., headache) not present at baseline.

Any deterioration in a laboratory value or other clinical test (e.g., ECG, X-ray) that is associated with symptoms or leads to a change in study treatment or concomitant treatment or discontinuation from study drug.

Adverse events that are related to a protocol-mandated intervention, including those that occur prior to assignment of study treatment (e.g., screening invasive procedures such as biopsies).

Adverse events that occur during or within 24 hours after study drug administration and are judged to be related to study drug infusion should be captured as a diagnosis (e.g., "infusion-related reaction" or "anaphylactic reaction") on the Adverse Event eCRF. If a patient experiences both a local and systemic reaction to the same dose of study drug, each reaction should be recorded separately on the Adverse Event eCRF. Associated signs and symptoms should be recorded on the dedicated Infusion-Related Reaction eCRF.

A pre-existing medical condition should be recorded as an adverse event only if the frequency, severity, or character of the condition worsens during the study (e.g., "more frequent headaches").

NOTE 1: Abnormal laboratory and vital signs values:

A laboratory test result must be reported as an adverse event if it is a change from baseline and meets any of the following criteria:

Is accompanied by clinical symptoms,

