- progression of disease. By convention, clinical events related to the primary cancer being studied or to the primary cancer progression are not to be reported as SAEs, even if they meet any of the seriousness criteria from the standard SAE definition, unless the event is more severe than expected and therefore the investigator considers that their clinical significance deserves reporting.

NOTE 3: Any laboratory abnormalities should be documented as a SAE if:

- Intensive treatment in an emergency room or at home for allergic bronchospasm is needed,
- Blood dyscrasias or convulsions that do not result in hospitalization,
- Any untoward event related, and unexpected, to the protocol procedures,
- The laboratory test result is clinically significant or meets the definition of a SAE,
- The laboratory abnormality required the participant to have study drug discontinued or interrupted,
- The laboratory abnormality required the subject to receive specific corrective therapy.

A SAE report should be completed for any event where doubt exists regarding its seriousness. Although overdose, pregnancy, AESI (e.g., potential drug-induced liver injury (DILI)), important medical event, and cancer (secondary malignancy) are not always serious by regulatory definition, these events must be handled as SAEs. If applicable, SAEs must be collected that relate to any later protocol-specified procedure (e.g., a follow-up skin biopsy).

If the investigator believes that a SAE is not related to study drug but is potentially related to the conditions of the study (such as withdrawal of previous therapy or a complication of a study procedure), the relationship should be specified in the narrative section of the SAE Report Form and an important medical event would be the seriousness.

All deaths that occur during the reporting period that are clearly the result of disease progression should not be reported as a SAE, but they should be collected as an AE. All deaths where it is not due to disease progression and deaths with an unknown cause should always be reported as a SAE.

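### Recording of non-serious adverse events can close before day 30 when treatment stops for progression, and it is unsettled whether deaths from progression enter the AE tables

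*Combined protocol and SAP*

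**What the plan says.** **AE window (section 8.1.5).** "End of treatment is defined as the day of discontinuation of the treatment". The safety follow-up visit is due within 30 days (± 3 days) of the last dose, "or immediately before the initiation of any other anticancer therapy". Its procedures are done at that visit, "or at the end of treatment when the cause is tumor progression". Under item 4, changes from baseline "should be recorded as adverse events on the Adverse Event eCRF until this visit". The same item continues: "SAEs and AESIs must be recorded and followed from the subject written informed consent signature to 30 days from last dose of treatment". No day count is attached to other AEs.

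**Other places that bear on the window.**
- Item 5 of the same list (concomitant medication) uses the same reference to the visit and equates it with 30 days from the last dose.
- Section 5 puts a safety follow-up one month after end of treatment, whatever the reason for stopping.
- Section 11.2 (management of anemia) asks for hematology at the end-of-treatment visit and again at 28 (± 5) days, with no exception for progression.

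**Deaths from progression.** Section 13.2 says that deaths in the reporting period that clearly result from progression "should not be reported as a SAE, but they should be collected as an AE". Section 13.1 leaves events that plainly fit the expected course of the disease out of the AE definition and adds: "These data will be captured as efficacy assessment data only". Doubtful cases are to be reported as AEs. Section 13.2 also says that death is an outcome, and that the event causing it is the term to report.

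**The concern.** Safety and tolerability by CTCAE-graded AEs is a secondary objective (section 4.2). The trial has one arm, so the absolute AE rate is itself the safety result, and any under-recording lowers that rate directly. As worded, section 8.1.5 gives patients who stop for progression, probably the largest group, a route to an earlier close of non-serious AE recording. Sites that follow item 4 literally and sites that follow section 5 would collect different data from similar patients.

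The second issue affects the count of fatal AEs. One site could enter a progression death on the AE form under 13.2, and another could leave it in the efficacy data under 13.1. The grade 5 row would then partly reflect which rule each site applied.

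**Working it through.** The plan gives no figure on this point, so there is none to reproduce. The check is a comparison of passages, with two illustrations of scale.

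**1. Which visit closes non-serious AE recording?**
- Item 4 ties the close to the visit at which the listed procedures are done.
- For a patient stopping for progression, that may be the end-of-treatment visit. End of treatment is the day of discontinuation and is not tied to a number of days from the last dose.
- Item 5, section 5 and section 11.2 each imply a contact at about 28 to 30 days or one month.
- The explicit 30-day limit in item 4 covers only SAEs and AESIs.

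The literal reading of item 4 therefore permits an earlier close, against three other places. What can be lost is late events that are neither serious nor AESIs.

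**2. How many days could be lost?** Days without required capture = 30 − day of the end-of-treatment visit after the last dose. Assume that this visit falls at the next dosing visit; the interval is 14 ± 3 days (section 10.1).

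| Visit on day | Days lost | Share of 30 |
|---|---|---|
| 11 | 30 − 11 = 19 | 63% |
| 14 | 30 − 14 = 16 | 53% |
| 17 | 30 − 17 = 13 | 43% |

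The extremes are 30 days lost if the visit is on the day of the last dose, and 0 if it is on day 30.

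**3. How many patients could be concerned?** Inputs from section 16: median PFS 4.5 months (alternative) or 3 months (null), dropout hazard 0.04, 47 patients. Assume exponential times and that the dropout hazard is per month. With λ = ln 2 / median, the share with progression or death before dropout is λ / (λ + 0.04).
- Median 4.5: λ = 0.154; 0.154 / 0.194 = 79%, about 37 of 47.
- Median 3: λ = 0.231; 0.231 / 0.271 = 85%, about 40 of 47.

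This is an upper guide. It counts deaths as well as progressions and ignores stops for toxicity.

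**4. Progression deaths.**
- 13.2 removes clear progression deaths from SAE reporting and collects them as AEs.
- Because death is an outcome, the event term for such a death would be the progression itself, or an event that fits it.
- That is the kind of event that 13.1 keeps out of the AE definition.
- As these deaths are not SAEs, the 30-day SAE rule does not cover them. They fall under ordinary AE recording, which by step 1 may already have closed at end of treatment in these patients.

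**The case against.** Several counter-arguments are fair.

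- **There is a benign reading.** Item 5 directly follows item 4 and treats the visit as day 30, and section 5 says that the cause of stopping does not matter. Use of the end-of-treatment visit is an option, not an order. This stands as evidence of what was probably meant. Item 4 still does not say it, and a site may act on the literal text.
- **Redaction.** Lines after the opening of 13.1, part of the SAE definition and most of the trial schedule are blacked out. An AE period may be stated there. If so, item 4 needs to match it.
- **13.1 does not mention deaths.** The conflict with 13.2 is an inference, and 13.2 can be read as the specific rule for deaths. That reading leaves open which event term may be used. Deaths not due to progression, or of unknown cause, are always SAEs, so possibly drug-related deaths are not at issue.

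A reader might also infer three stronger claims that the documents do not support:
- **That only progressors can have recording closed early.** Any patient who starts other anticancer therapy can have the safety visit before day 30. Only the move to the end-of-treatment visit is specific to progression.
- **That the safety endpoint is distorted.** SAEs and AESIs keep 30 days in all patients, no between-arm comparison can be biased, and the number of missed events cannot be derived.
- **That the effect on the fatal-AE rate can be quantified.** This needs survival after progression, which the documents do not give, and the relevant period is the days left after the end-of-treatment visit, not a full month after progression.

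**Conclusion.** The point holds as two inconsistencies to be reconciled. First, section 8.1.5 permits recording of non-serious, non-AESI events to close before day 30 in patients who stop for progression, contrary to section 5, item 5 and section 11.2. The possible loss is 13 to 19 of 30 days, if the end-of-treatment visit falls at the next dosing visit. The consequence is possible under-capture of late non-serious events; its effect on the reported AE rate is unknown. Second, 13.1 and 13.2 leave it unsettled whether clear progression deaths appear in the AE tables, so the grade 5 count is not fully defined. Both conclusions rest on the visible text, since redacted lines may state an AE period. No sample size, power or efficacy figure is affected.

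**What to change.** - **Section 8.1.5, item 4:** record all AEs to 30 days after the last dose, or to the start of new anticancer therapy if earlier, in every patient whatever the reason for stopping. Leave the 30-day rule for SAEs and AESIs as it is. Make a telephone contact when the visit is held early. Match the wording to section 5, section 11.2 and any AE period stated in 13.1.
- **Reporting:** because the new-therapy cut-off still shortens the window for some patients, state how many were cut short.
- **Sections 13.1 and 13.2:** write one rule for deaths clearly due to progression, including the event term to use, and tabulate them separately from other grade 5 AEs.

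The cost is small: wording changes in two sections and one extra call for some patients, in a trial that already has telephone follow-up. The reported AE rate may be slightly higher.

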9.1. Packaging and labelling

Merck will provide the IMP Bintralusp alfa (M7824) at no cost for this study. Clinical supplies will be affixed with a clinical label in accordance with regulatory requirements.

The Bintralusp alfa (M7824) drug product is provided as a sterile concentrate solution for infusion 10m/ml in single-use glass vials. The vial is designed to allow an extractable volume of 60 mL (600 mg/60 mL). For further details on the formulation and handling of Bintralusp alfa (M7824), see the **BIMES drug supply manual** and Investigator's Brochure of the IMP.

9.2. Receipt and storage of the IMP

Accurate records of the IMP received at, dispensed from, returned to, and disposed of by the study site should be recorded on the Drug Accountability Log. In the event that the IMPs are destroyed a certification of destruction form should be generated and retained in the Pharmacy Site File.

The IMPs must be stored in a secure area according to local regulations. The investigator must ensure that the IMPs are stored refrigerated at 2-8°C, protected from light and freezing, see the **BIMES drug supply manual** for details.

9.3. Unused trial drug supplies

If the IMPs are to be destroyed, it is the investigator's responsibility to ensure that arrangements have been made for disposal and that procedures for proper disposal have been established according to applicable regulations, guidelines, and institutional procedures. Appropriate records of the disposal must be maintained. Provide a certificate of destruction to Fundación GECP upon disposal. See the **BIMES drug supply manual** for details.

10. Trial treatments description

10.1. BINTRALUSP alfa (M7824)

Patients will receive 1200 mg of M7824 administered once every 14 days (+/- 3 days) over 60 minutes (+/- 10-20 minutes) intravenous infusion in a monitored setting where there is immediate access to trained personnel and adequate equipment/medicine to manage potentially serious reactions.

Refer to **BIMES drug supply manual** for detailed instructions on drug preparation, storage, and administration.

11. Dose modifications criteria

Doses cannot be delayed beyond the treatment window. Participants must skip dose if the treatment window is missed. Doses can be omitted until a maximum time of 8 weeks, for longer periods of time, the Trial Chair must be consulted. Reasons for dose delays, the supportive measures taken, and the outcomes will be documented in the patient's chart and recorded on the eCRF.

11.1. General Notes Regarding Dose Modification

When several toxicities with different grades of severity occur at the same time, the dose modifications should be according to the highest grade observed.

The investigator may use discretion in modifying or accelerating the dose modification guidelines depending on the severity of toxicity and an assessment of the risk versus benefit for the patient, with the goal of maximizing patient compliance and access to supportive care.

11.2. BINTRAFUSP (M7824). Toxicity Management

Treatment modification guidance for symptoms of infusion-related reactions including immediate hypersensitivity:

| NCI-CTCAE Grade | Treatment Modification |
|--|---|
| Grade 1 - mild Mild transient reaction; in general, infusion interruption not indicated; intervention not indicated | 
• Increase monitoring of vital signs as medically indicated as participants are deemed medically stable by the attending Investigator.• Hold infusion if deemed necessary by the investigator. |
| Grade 2 – moderate Therapy or infusion interruption indicated but responds promptly to symptomatic treatment (for example, antihistamines, nonsteroidal anti-inflammatory drugs, narcotics, IV fluids); prophylactic medications indicated for ≤ 24 h. | 
• Stop the infusion of the study intervention.• Increase monitoring of vital signs as medically indicated as participants are deemed medically stable by the attending Investigator.• If symptoms resolve quickly, resume infusion at 50% of original rate with close monitoring of any worsening signs and symptoms, otherwise dosing held until resolution of symptoms with mandated premedication for the next scheduled visit.• If not improving, consider administration of glucocorticoids and stop the infusion for that day.• If the participant has a second IRR Grade ≥ 2 on the slower infusion rate despite premedication, the infusion should be stopped, and the investigator may consider withdrawal of this participant from the study. |
| Grade 3 or Grade 4 – severe or life-threatening 
○ Grade 3: Prolonged (for example, not rapidly responsive to symptomatic medication and/or brief interruption of infusion); recurrence of symptoms following initial improvement; hospitalization indicated for clinical sequelae.○ Grade 4: Life-threatening consequences; urgent intervention indicated. | 
• Stop the infusion of study intervention immediately and disconnect infusion tubing from the participant with additional appropriate medical measures and closely monitor until deemed medically stable by the attending Investigator. Hospitalization and/or close monitoring is recommended• Administration of glucocorticoids may be required• For Grade 3 or 4 IRRs, permanent discontinuation of study intervention is mandated. |

Once the infusion is interrupted or rate reduced to 50% of previous infusion rate, it must remain decreased for all subsequent infusions.

For all types and grades of infusion reactions, details about drug physical constitution, method of preparation, and infusion must be recorded.

Participants should be instructed to report any delayed reaction immediately.

IRR=infusion-related reactions, IV=intravenous, NCI-CTCAE=National Cancer Institute-Common Terminology Criteria for Adverse Event, NSAIDs=nonsteroidal anti-inflammatory drugs.

Management of immune-mediated adverse events

Immune-related AEs are specific to immunotherapies and vary by organ system. Immune-related AEs are important identified risks for bintralafusp alfa.

Recommended guidance and management for specific irAEs are provided in the current NCCN guideline available at <http://www.nccn.org>.

Requirements in addition to NCCN guidelines:

- Permanent treatment discontinuation is required in case of immune-related Grade 4 rash/inflammatory dermatitis, nephritis, autoimmune hemolytic anemia, hemolytic uremic syndrome, aplastic anemia, immune thrombocytopenia, acquired thrombotic thrombocytopenic purpura inflammatory arthritis, myositis and polymyalgia-like syndrome.
- For Grade 4 immune-related lymphopenia, permanent treatment discontinuation will be required, if lymphopenia is considered immune-related in nature, no clear alternative explanation exists for the event, and it does not resolve within 14 days. Permanent treatment discontinuation is not required when the AE is manifested by a single laboratory value out of normal range without any clinical correlates. In this case, treatment should be held until the etiology is determined. If the event is not considered immune-related and resolves to Grade ≤ 1 , restarting treatment may be considered.
- For Grade 1 immune-related pneumonitis: continue treatment. If clinically indicated, monitor participants weekly or more frequently as needed with history, physical examination and pulse oximetry. If symptoms appear and/or changes in the physical exam are noted, treat as Grade 2.
- For myositis: in case of management with rituximab, treatment should be discontinued.

Management of TGF- β mediated Skin Adverse Events

Skin assessment must be performed at baseline and at least every 6 weeks during treatment and at the end of treatment or 28 (± 5 days) days post-treatment safety follow-up (if not performed in the previous 6 weeks).

- Hyperkeratosis
- Keratoacanthoma
- Cutaneous squamous cell carcinoma (cSCC)
- Basal cell carcinoma
- Actinic keratosis

Management

- Baseline skin assessment with detailed medical history
- Discontinuation or termination not required in most cases. Continuation of treatment should be evaluated by the Investigator.
- Emollients may be used
- Develop diagnostic and treatment plan in collaboration with Investigator and dermatologist
- Treatment follow-up will depend on number and localization of lesions.
 - Single lesion: full excision may be recommended
 - Multiple lesion or location not suitable for full excision: Mohrs surgery, cryotherapy or other standard treatment options depending on pathology. Topical retinoids may be used after discussion with Investigator.
- Close clinical follow-up for re-evaluation, resolution and potential recurrence should be implemented
- In general, treatment of TGF- β mediated skin lesions should be based on local guidelines/standard of care.

Additional consideration: Keratoacanthoma lesions may resolve spontaneously without surgical intervention within weeks after discontinuing bintrafusp alfa.

Consult with Medical Monitor as needed for management of TGF- β mediated skin lesions.

Management of Anemia

- Anemia is considered an important identified risk for bintrafusp alfa.
- Hematology assessment must be performed at baseline, prior to each bintrafusp alfa dose, at the end of treatment visit and at 28 (± 5 days) days post-treatment safety follow-up.
- Participants must enter the study with Hgb values at least 9g/dl
- All relevant hematological testing for treatment-related anemias should be done prior to a blood transfusion, if clinically feasible

Basic Anemia Evaluation

- CBC with emphasis on red cell indices
- If indicated and at clinical discretion, the following should be considered:
 - Iron studies
 - Serum Folate and Vit B12 values
 - Coagulation factors
 - Fecal occult blood
 - Urinalysis
 - Hormone panel: TSH, Erythropoietin
 - Peripheral blood smear

Further Recommendation Based on Suspected Etiology (in Addition to Basic Anemia Testing)

- Suspected Hemolysis
 - bilirubin, LDH, Coombs test, haptoglobin
- Suspected bleeding:
 - Consider imaging/interventional radiology consultation as indicated
 - Consider imaging and/or endoscopy as clinically indicated
- Suspected aplastic anemia:
 - Hematology consultation
 - Consider bone marrow aspiration/morphologic evaluation

Additional consideration:

In general, blood transfusions and erythroid growth factors are permitted as clinically indicated.

Abbreviation: CBC: complete blood count, TSH: thyroid stimulating hormone, LDH: lactate dehydrogenase

Management of Mucosal/Non-tumor and Tumor Bleeding

| Mucosal Bleeding | |
|--|--|
| 
Events of mild to moderate severity are a potential risk for binrafusp alfa.In general, these reactions resolve without discontinuation of treatment.Events may include, but are not limited to the following:
EpistaxisHemoptysisGingival bleedingHematuria | |
| Mucosal/Non-tumor Bleeding | |
| Grading | Management |
| Grade 2 | 
If resolves to Grade ≤ 1 by the day before the next infusion, study intervention may be continuedIf not resolved to Grade ≤ 1 by the day before the next infusion, but is manageable and /or not clinically relevant, consult Medical Monitor to assess if clinically reasonable to administer the following infusion. |
| Grade ≥ 3 | 
Permanently discontinue treatment unless an alternative explanation can be identified (such as concomitant use of antithrombotic agents, traumatic events, etc.)In case of alternative explanations, hold study treatment until the event recovers to Grade ≤ 1If Grade ≥ 3 bleeding event is observed, regardless of causality with the study intervention, upon resumption of study intervention binrafusp alfa dose should be reduced by 50% (600 mg Q2W. Once there is stable resolution and no recurrence of bleeding on reduced dose, Investigator is encouraged to communicate with sponsor on potential dose re-escalation after careful benefit-risk assessment |
| Grade 4 | 
Treatment must be permanently discontinued if no alternative explanation is identified. |

| | |
|---|--|
| 
In case of rapid decrease of hemoglobin (Hgb), such as a decrease greater than 2.0 g/dL across a 2 weeks period, withhold the subsequent cycles of study intervention until Hgb is stabilized and do a thorough assessment of bleeding (for example, upper and lower GI endoscopy, enhancement CT etc.); if Grade 1 or greater bleeding is observed or suspected, withhold the bintrafusp alfa until the bleeding is resolved/controlled and resume the dose of bintrafusp alfa reduced by 50%. Once Hgb decrease is recovered to \leq Grade 1 or baseline and stably controlled, the Investigator is encouraged to communicate with Medical Monitor to re-escalate the dose. The dose of bintrafusp alfa may be re-escalated to full dose once Hgb is stabilized without further need for blood transfusion in the subsequent cycles. The timing of re escalation may need a case-by-case decision. See Section Table on Management of anemia | |
| Tumor Bleeding | |
| Grade \geq 2 | 
Study treatment must be held till the event recovers to Grade \leq 1Permanently discontinue treatment if the Investigator considers the participant to be at risk for additional severe bleeding. |
| Grade \geq 3 | 
If Grade \geq 3 bleeding event had been observed, regardless of causality with the study intervention, upon resumption of the study intervention bintrafusp alfa dose should be reduced by 50%. Once there is stable resolution and no recurrence of bleeding on reduced dose, Investigator is encouraged to communicate with the sponsor potential dose re-escalation after careful benefit-risk assessment. Treatment should be permanently discontinued if the Investigator considers the participant to be at risk for additional severe bleeding.In case of rapid decrease of hemoglobin (Hgb), see Section Mucosal/Non-Tumor bleeding. |

Impaired Wound Healing

- Impaired wound healing is considered important potential risk for bintrafusp alfa
- Management should be discussed with Medical Monitor for participants requiring surgery on study.
- It is recommended to hold study intervention for approximately 4 weeks post major surgery for observation.
- Post-operative wound healing should be closely monitored

12. Prohibited and permitted concomitant treatments

Concomitant therapy consists of any medication (e.g., prescription drugs, over-the-counter drugs, vaccines, herbal or homeopathic remedies, nutritional supplements) used by a patient in addition to protocol-mandated treatment from 7 days prior to initiation of study drug to the study completion/discontinuation visit. All such medications should be reported to the investigator and recorded on the Concomitant Medications form in the eCRF.

Prohibited Concomitant Therapy

The following medications are prohibited while on study, unless otherwise noted:

- Cytoreductive therapy
- Radiotherapy delivered for non-palliative indications
- Immunotherapy, immunosuppressive drugs (that is, chemotherapy or systemic corticosteroids except for short-term treatment of allergic reactions or for the treatment of irAEs), or other experimental pharmaceutical products. Short-term administration of systemic steroid (that is, for allergic reactions or the management of irAEs is allowed).
- Live vaccine administration within 30 days before M7824. Vaccination with live vaccines while on study is prohibited. Administration of inactivated vaccines is allowed (for example, inactivated influenza vaccines)

The concomitant use of herbal therapies is not recommended because their pharmacokinetics, safety profiles, and potential drug-drug interactions are generally unknown. However, their use for patients on study is allowed at the discretion of the investigator provided that there are no known interactions with any study treatment. As noted above, herbal therapies intended for the treatment of cancer are prohibited.

Permitted Concomitant Therapy

Premedication with antihistamines may be administered for any M7824 infusions before day 1 week 1 and week 3. The following therapies should continue while patients are on study:

- Oral contraceptives.
- Hormone-replacement therapy.
- Prophylactic or therapeutic anticoagulation therapy, such as low molecular weight heparin (preferred) or warfarin at a stable dose level.
- Inactive influenza vaccinations.
- COVID-19 vaccination with an approved vaccine is allowed for patients included in the study
- Megestrol administered as an appetite stimulant.

- Inhaled corticosteroids for chronic obstructive pulmonary disease.
- Mineralocorticoids (e.g., fludrocortisone).
- Low-dose corticosteroids for patients with orthostatic hypotension or adrenocortical insufficiency (e.g. oral hidroaltesona 20 mg per day).
- G-CSF is allowed as per local standard.
- Any medications (other than those excluded by the exclusion criteria or the prohibited medicines) that are considered necessary for the participants' welfare and will not interfere with the study intervention may be given at the Investigator's discretion.
- Other drugs to be used for prophylaxis, treatment of hypersensitivity reactions, and treatment of fever or flu-like symptoms

In general, investigators should manage a patient's care with supportive therapies as clinically indicated per local standards. Patients who experience infusion-associated symptoms may be treated symptomatically with acetaminophen, ibuprofen, diphenhydramine, and/or famotidine or another H2-receptor antagonist per standard practice. Serious infusion-associated events manifested by dyspnea, hypotension, wheezing, bronchospasm, tachycardia, reduced oxygen saturation, or respiratory distress should be managed with supportive therapies as clinically indicated (e.g., supplemental oxygen and β 2-adrenergic agonists).

Cautionary Concomitant Therapy

Systemic corticosteroids and TNF- α inhibitors may attenuate potential beneficial immunologic effects of treatment with binrafusp alfa. Therefore, in situations where systemic corticosteroids or TNF- α inhibitors would be routinely administered, alternatives, including antihistamines, should be considered first by the treating physician. If the alternatives are not feasible, systemic corticosteroids and TNF- α inhibitors may be administered at the discretion of the treating physician except in the case of patients for whom CT scans with contrast are contraindicated (i.e., patients with contrast allergy or impaired renal clearance).

Systemic corticosteroids are recommended, with caution at the discretion of the treating physician, for the treatment of specific adverse events when associated with binrafusp alfa therapy. Guidelines for the management of immune-mediated adverse events are described in Appendix 7.

13. Adverse events and reporting

